2.3 Study Subjects

2.3.1 Subject disposition

The number and percentage of subjects in each study population (FAS, PP, and Safety) will be summarized by site (including subject number) and in total (Table 4-1). Study population variables will also be presented in a data listing.

The disposition of subjects (Table 4-4) will be presented by site, and in total, including number and percentage of subjects that were

- screened
- treated,
- completed,
- withdrawn.

The number of completed and withdrawn subjects will also be accounted for by visit, along with number of expected subjects, number of screening failures, number of treated subjects, and subjects with performed WSRS assessment (Table 4-5).

Reasons for screening failures and withdrawals, if applicable, will be summarized. All withdrawn subjects will be listed individually, including site and subject number, date of treatment, last visit performed, date and reason for withdrawal (Table 4-7). Screening failures

 GALDERMA	Title SAP, 43CH1508, Restylane Defyne NLF	Doc id MA-31549
--	--	----------------------------------

will be listed by site number, subject screening number, date of screening, and reason for screening failure (Table 4-6).

2.3.2 *Protocol deviations*

Subjects with CSP deviations will be listed individually, including subject number and observed deviation, and visit number if applicable (Table 4-3). Depending on the seriousness of the deviation, the subject might be excluded from the PP population (Table 4-2), which shall be documented prior to database lock (DBL).

Definition of protocol deviations that will exclude subjects from the PP are defined (but not limited to) in Table 2-1 below.

Table 2-1: Protocol deviations

Deviation	
GENERAL	
	Visit out-of-window
*	Follow-up at 6 months after last treatment performed earlier than 1 week before the scheduled visit or later than 2 weeks after the scheduled visit.
	Visit not done
*	Follow-up at 6 months not done.
EFFICACY	
	WSRS assessed by Blinded Evaluator
*	Not done for both NLFs at 6 months after last treatment.
*	Pre-treatment WSRS not available for both NLFs.
OTHER	
	Inclusion/exclusion criteria
*	Any inclusion criteria affecting primary efficacy evaluation not met.
*	Any exclusion criteria affecting primary efficacy evaluation met.
	Treatment
*	Same product administered in both NLFs at initial treatment or touch-up.
*	Products administered in the wrong sides at initial treatment or touch-up.

 GALDERMA	Title SAP, 43CH1508, Restylane Defyne NLF	Doc id MA-31549
--	--	----------------------------------

Effective date: 2017-02-13 08:27

Effective

Version: 1.0

2.3.3 *Demographics and Baseline characteristics*

Demographic endpoints and subject baseline characteristics will be presented overall (Table 5-1) using descriptive statistics. Gender, ethnic origin, and Baseline WSRS score will be analyzed as categorical end points using number and percentage of subjects. Age and vital sign tests will be summarized by number of subjects, mean, standard deviation, minimum, median, and maximum values. Pre-treatment procedures will be summarized as categorical endpoints by treatment visit (Table 5-2).

2.3.4 *Medical history, and concomitant medication and procedures/treatments*

All summaries will be based on the FAS population. Concomitant medications will be coded using the World Health Organization (WHO) Drug Dictionary. Medical history will be coded according to medical dictionary for regulatory activities (MedDRA).

Medical history/concurrent disease

The number and percentage of subjects reporting any medical history/concurrent disease (relevant or major illness), (Table 5-3), and any previous cosmetic/aesthetic procedures or implants (Table 5-5) will be presented in total.

The number and percentage of subjects reporting medical history/concurrent disease (relevant or major illness), and the number of events will be summarized by System Organ Class (SOC) and in total, for all medical history during the whole study and ongoing at study start (Table 5-4).

Previous cosmetic/aesthetic or implant procedures will be summarized by procedure/product name and procedure/product location using number and percentage of subjects (Table 5-6).

Concomitant medication and procedures/treatments

The number and percentage of subjects reporting concomitant medication ongoing at study start, initiated during study and in total (Table 6-1) will be summarized. In addition, the number and percentage of subjects reporting concomitant medication, and the number of medications (all during study and the number of ongoing medications at study end), will be summarized by reason and in total (Table 6-2). Also, the number and percentage of subjects, and the number of medications, will be summarized by ATC code and in total, along with an ATC text description for medication ongoing at study start (Table 6-3) and initiated during study (Table 6-4).

Concomitant medication taken due to an AE will be summarized by ATC code (along with an ATC text description) and in total using number and percentage of subjects and number of medications, and by MedDRA coded AE and whether the AE is related or not (Table 6-5).

 GALDERMA	Title SAP, 43CH1508, Restylane Defyne NLF	Doc id MA-31549
--	---	---------------------------

Concomitant procedures/treatments will be presented using number and percentage of subjects (Table 6-6), as well as by reason and in total using number and percentage of subjects and number of procedures/treatments (Table 6-7).

2.3.5 *Extent of exposure*

Injection volume (mL), for each treatment visit and in total will be presented by treatment (Table 7-1) using number of subjects, mean, standard deviation, minimum, median, and maximum values. The same summary will also be generated by site and in total (Table 7-4). Within-subject difference (Restylane minus Restylane Defyne) of injected volume (mL) will be presented by treatment visit and in total by number of subjects, mean, standard deviation, minimum, median, and maximum values (Table 7-2).

Injection time (minutes) for each treatment and within-subject difference (Restylane minus Restylane Defyne) in injection time (minutes) will be summarized using number of subjects, mean, standard deviation, minimum, median, and maximum values (Table 7-3).

Optional touch-up treatment eligibility evaluation (No/Yes) after initial treatment will be summarized by 3 eligibility questions using number and percentage of subjects (Table 7-5). In addition, number and percentage of subjects receiving touch-up treatment will be presented.

Number and percentage of subjects in each category and in total for injection method (Table 7-6), injection depth (Table 7-7), topical/local anesthesia used (Table 7-8), post-treatment care (Table 7-9), technical problems/device deficiencies (Table 7-10), deviations from the treatment procedure (Table 7-11), and directly observed AEs associated with the injection (Table 7-12) will be presented by treatment visit and treatment.

2.4 Efficacy Analysis

2.4.1 *Data sets analyzed*

All efficacy variables will be analyzed using the FAS population. The primary analysis will be repeated using the PP population. If it is deemed necessary, other analyses will be repeated using the PP population.

2.4.2 *Handling of missing data*

As the study design is intra-individual, in which the outcome of both treatments to be compared is available on each subject, it is expected that when a data is missing, it will be missing for both NLFs in most of the cases. A majority of the deviations from the protocol can be expected to affect both NLFs and evaluations of the same subject the same way.

 GALDERMA	Title SAP, 43CH1508, Restylane Defyne NLF	Doc id MA-31549
--	--	----------------------------------

Effective date: 2017-02-13 08:27

Effective

Version: 1.0

FAS analyses of WSRS scores in the primary analysis will use multiple imputation method (MI) as the primary method for imputing missing values. Rather than imputing each missing observation by a single value, this approach represents a random sample of the missing values, and therefore accounts for the prediction uncertainty of the unknown missing values. Last observation carried forward (LOCF) will be used as an alternative imputation method.

Safety and PP analyses will be presented based on observed cases, i.e., no imputation of missing values will be performed.

(i) Use of MI

The imputation using MI will assume a Missing Completely at Random (MAR) mechanism. The MI procedure of the SAS® system will be used to generate five sets of data with missing values imputed from observed data. It is expected that the pattern of missing data will be monotonic, with slight deviations being corrected by the Markov Chain Monte Carlo (MCMC) method of the MI procedure. Linear regression will be employed to model the missing WSRS score, with the following covariates included in the imputation model: treatment and non-missing data from earlier time points (Baseline, Week 2, and Month 3). The imputed datasets will be analyzed using the methodology described for the primary analysis of response rates at Month 6. The results from the analysis of the multiple imputed datasets will be presented as appropriate. The seed number to be used will be 431508.

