1.1.2 Number of subjects and randomization

Approximately 175 subjects will be enrolled and treated with Restylane Defyne in one NLF and Restylane in the opposite NLF, as randomly assigned to one of the two possible treatment sequences:

[figure not shown]
- Restylane Defyne in the subject's right NLF followed by Restylane in the subject's left NLF, or
- Restylane in the subject's right NLF followed by Restylane Defyne in the subject's left NLF.

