2.1 General Methods

All statistical analyses, including summary tables and data listings, will be performed using the SAS® system (version 9). Confidence intervals will be two-sided and constructed at the 95% confidence level.

Continuous endpoints will be summarized using descriptive statistics, e.g., mean, median, standard deviation, minimum, and maximum values. Categorical endpoints will be presented in frequency tables with number and percentage of observations for each level.

Table/graph shells of data summaries are provided in Appendix A-F and are referenced to in the text. All graphs are only examples and will be updated in the Statistical Analysis Report (SAR) to reflect the study data. Any change made to the finalized Statistical Analysis Plan (SAP) will be documented in the Clinical Study Report (CSR).

 GALDERMA	Title SAP, 43CH1508, Restylane Defyne NLF	Doc id MA-31549
---	--	--------------------

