2.4.3 Primary analysis

Non-inferiority testing of Restylane Defyne relative to Restylane will be assessed on the 95% confidence interval approach with a non-inferiority margin of 15%. The confidence interval will be constructed for the difference (Restylane minus Restylane Defyne) in response rates at the 6 months follow-up visit (Table 8-1 and Table 8-2). Non-inferiority will be declared if the two-sided 95% interval is fully below 15%, i.e., the upper bound of the interval is less than 15% in both the FAS and PP populations.

To assess the robustness of the results using the MI method, LOCF will be used as an alternative imputation method. The same summary of primary analysis results will also be presented for observed cases (OC), (Table 8-1).

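### Five imputations leave an avoidable seed-to-seed error in the FAS non-inferiority bound (SD about 0.4-0.8 points if 5-10% of Month 6 data are missing); 50-100 imputations would cut it to about 0.1-0.2

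*SAP*

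**What the plan says.** SAP 2.4.2 makes multiple imputation the primary way of handling missing WSRS scores in the FAS. Under (i), the SAS MI procedure "will be used to generate five sets of data with missing values imputed from observed data". The seed is set in advance: "The seed number to be used will be 431508". The model is also given: "Linear regression will be employed to model the missing WSRS score, with the following covariates included in the imputation model: treatment and non-missing data", the latter taken at visits before Month 6. No reason is given for choosing five, and no report of Monte Carlo error is planned.

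The imputed result feeds a threshold rule. SAP 2.1 states: "Confidence intervals will be two-sided and constructed at the 95% confidence level". SAP 2.4.3 takes the difference as Restylane minus Restylane Defyne and declares non-inferiority if "the upper bound of the interval is less than 15% in both the FAS and PP populations". Table 8-1 labels the MI row as primary and places the LOCF and observed-case results beneath it as sensitivity analyses. The PP result does not involve imputation: "Safety and PP analyses will be presented based on observed cases, i.e., no imputation of missing values will be performed".

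**The concern.** Each multiple-imputation run is a random sample of completed data sets. With five of them, the pooled difference averages only five draws, and the between-imputation variance, which sets part of the interval's width, is estimated on four degrees of freedom. Both parts of the upper bound therefore carry simulation noise that comes from the random-number stream and not from the patients.

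High relative efficiency at five imputations does not settle this. It says that the long-run variance of the estimate is barely inflated. It does not say how far the one bound that is reported would have moved under another, equally valid seed. Because that bound is compared with a fixed 15%, such noise should be negligible, and it can be made so for seconds of computing.

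**Working it through.** **Inputs from the documents.** Five imputations, seed 431508 and the linear-regression imputation model (SAP 2.4.2); about 175 subjects, each contributing both folds (SAP 1.1.2); two-sided 95% interval (SAP 2.1); 15-point margin, to be met in FAS and PP (SAP 2.4.3).

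**Assumed inputs.** The visible text gives no missing-data rate, response rate or within-subject correlation, and the sample-size sections are redacted. I took 3-20% missing, mostly on both folds together as SAP 2.4.2 expects, response rates of about 64-80% and within-subject correlations of about 0.2-0.5. Pooling by Rubin's rules with a t reference and a paired Wald variance is also assumed, because the SAP does not name the pooling formula or the interval method. There is no stated Monte Carlo error to reproduce.

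**Step 1: formula check.** Let p be the response rate, ρ the correlation, N the number of subjects, f the fraction missing and m the number of imputations.

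- Variance of the within-subject difference: 2p(1−p)(1−ρ). With p = 0.7 and ρ = 0.5 this is 2 × 0.7 × 0.3 × 0.5 = 0.21.
- Complete-data variance of the mean difference: U = 0.21/175 = 0.0012.
- Between-imputation variance, ignoring covariates: B ≈ U × f/(1−f).
- Seed-to-seed SD of the point estimate: √(B/m).
- Seed-to-seed SD of the half-width 1.96√T, with T = U + (1+1/m)B: about 1.96 × (1+1/m)/(2√T) × B√(2/(m−1)).

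At f = 0.10 and m = 5, B = 0.0012 × 0.1/0.9 = 0.000133. The point-estimate part is √(0.000133/5) = 0.52 points. For the width, T = 0.0012 + 1.2 × 0.000133 = 0.00136 and √T = 0.0369, giving 1.96 × 1.2/(2 × 0.0369) × 0.000133 × 0.707 = 0.30 points. Together: √(0.52² + 0.30²) = 0.60 points.

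| Missing | m = 5 | m = 50 | m = 100 |
|---|---|---|---|
| 5% | 0.38 | 0.12 | 0.08 |
| 10% | 0.60 | 0.18 | 0.13 |

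(SD of the upper bound across seeds, in percentage points.)

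**Step 2: simulation close to the SAP model.** Paired WSRS scores for 175 subjects with near-monotone missingness were imputed by Bayesian linear regression on treatment, baseline, first follow-up and Month 3. The first follow-up stands in for the Week 2 covariate listed in the SAP, because the protocol schedule has no Week 2 visit. Each fixed data set was re-imputed under 200 to 300 seeds at m = 5, and under fewer at larger m, with folds imputed separately or jointly.

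| Missing | SD, m = 5 | 95% spread, m = 5 | Mean gap between two seeds, m = 5 |
|---|---|---|---|
| 3% | 0.3-0.4 | 1.1-1.4 | 0.3-0.4 |
| 5% | 0.4-0.5 | 1.6-2.1 | 0.5 |
| 10% | 0.7-0.8 | 2.5-3.3 | 0.8 |
| 15% | 0.9-1.1 | 3.5-4.5 | 1.0 |

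At 5% missing the SD falls to 0.14-0.16 with m = 50 and 0.07-0.11 with m = 100. At 10% missing it falls to 0.20-0.24 and 0.14-0.16.

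**Step 3: a second imputation scheme.** Drawing missing response pairs directly, with no earlier visits, at 80% versus 78% response, ρ = 0.5 and 10% missing, gave SDs of 0.61 (m = 5) and 0.13 (m = 100). With folds drawn independently they were 0.86 and 0.17. The size of the effect does not hinge on the imputation model.

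**Step 4: could the verdict change?** In the Step 3 setting the bound centres near 9.0-9.5 points, with a sampling SE of about 3.25. The chance that two seeds give different FAS verdicts is roughly the density of the bound at 15 times the mean gap between seeds (2 × SD/√π).

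- Centre 9.0, SD 0.61: density 0.0223 × gap 0.69 = 1.5%.
- Centre 9.5, SD 0.86: density 0.0293 × gap 0.97 = 2.8%.

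At 5% missing the same calculation gives under 1%.

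**The case against.** The strongest reply is that this is tuning. The seed is written into the SAP, so the same data and program return the same number and nobody can shop for a favourable one. The PP result must also pass and contains no imputation, so a lucky draw alone cannot make the trial positive. The LOCF and observed-case FAS results are seed-free and sit beside the MI result, so an outlying MI bound would be noticed. Under the assumptions used, the simulated bounds averaged about 5-11%, well short of 15%.

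All of that stands, and it limits the importance of the point. It does not remove it. Fixing the seed makes the draw repeatable but no less arbitrary. The SAP does not state data layout, sort order or MCMC settings, so an independent programmer using the same seed could obtain different imputations. And because both populations must pass, an unlucky FAS draw could still fail the trial.

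A reader might infer more than the documents support:

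- **That the bound moves by two to three points with the seed.** That is the full 95% spread at roughly 6-10% missing. The visible documents give no missing rate, the spread is smaller at 3-5%, and two seeds typically differ by only 0.3-0.8 points at 3-10% missing.
- **That more imputations would eliminate the error.** It shrinks roughly as 1/√m, so going from 5 to 100 cuts it about 4.5- to 5-fold (√20 ≈ 4.5).
- **That the seed decides the trial.** The dual FAS and PP requirement and the figures in Step 4 contradict this.

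**Conclusion.** The point holds as a minor one. Given 5-10% missing Month 6 assessments, five imputations leave a seed-to-seed SD of about 0.4-0.8 points in the FAS upper bound (95% spread about 1.6-3.3 points), and 50-100 imputations reduce the SD to about 0.1-0.2. The FAS verdict is exposed only if the bound falls within about 1-2 points of 15%. These sizes rest on the assumed missing rate, response rates, correlation and pooling method. They would be smaller with fewer missing data and larger at 15% or more. Nothing here suggests bias or any freedom to select a result.

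**What to change.** In SAP 2.4.2 (i), replace five by 100 imputed data sets (50 at the least) and keep seed 431508. Estimand, margin, populations and imputation model stay as they are.

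The cost is one number in the SAP, one option in the MI call and seconds of computing, plus the paperwork: the SAP is already an effective version 1.0, and its section 2.1 requires any change to the finalized plan to be recorded in the clinical study report. Make the change before database lock, because raising the number after seeing a bound near 15% would look post hoc.

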1.3 Efficacy Assessments

1.3.1 Wrinkle Severity Rating Scale (WSRS)

WSRS is a 5-grade validated photograph-based scale designed for quantifying facial folds. Scoring of fold severity is based on a visual assessment of the length and depth of the NLF at a certain time point, not in comparison to the Baseline or pre-treatment appearance, see Table 1-1. Each score in the WSRS is exemplified by a photograph of NLFs.

 GALDERMA	Title SAP, 43CH1508, Restylane Defyne NLF	Doc id MA-31549
---	--	--------------------

Table 1-1: Wrinkle Severity Rating Scale (WSRS)

Grade	Description
1	Absent: No visible fold; continuous skin line.
2	Mild: Shallow but visible fold with a slight indentation; minor facial feature. Implant is expected to produce a slight improvement in appearance.
3	Moderate: Moderately deep fold; clear facial feature visible at normal appearance but not when stretched. Excellent correction is expected from injectable implant.
4	Severe: Very long and deep fold; prominent facial feature; less than 2 mm visible fold when stretched. Significant improvement is expected from injectable implant.
5	Extreme: Extremely deep and long fold; detrimental to facial appearance; 2 to 4 mm V-shaped fold when stretched. Unlikely to have satisfactory correction with injectable implant alone.

The Blinded Evaluator will perform assessment of each NLF using the WSRS at Screening, Baseline, and each follow-up visit.

CCI

 GALDERMA	Title SAP, 43CH1508, Restylane Defyne NLF	Doc id MA-31549
--	--	----------------------------------

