1.4 Efficacy Endpoints

1.4.1 Primary efficacy endpoint

The primary efficacy endpoint is the response rate based on the WSRS score, as assessed by the Blinded Evaluator at 6 months after last treatment.

Response rate is defined as the percentage of subjects with at least one (≥ 1) grade improvement on the WSRS.

 GALDERMA	Title SAP, 43CH1508, Restylane Defyne NLF	Doc id MA-31549
---	--	--------------------

Effective date:

2017-02-13 08:27

Effective

CCI

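### The primary multiple imputation draws continuous WSRS scores and never returns them to whole grades, so both products' primary FAS response rates come out too low when Month 6 scores are missing.

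*SAP*

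**What the plan says.** SAP 1.3.1 describes the scale: "WSRS is a 5-grade validated photograph-based scale designed for quantifying facial folds". SAP 1.4.1 defines the endpoint: "Response rate is defined as the percentage of subjects with at least one (≥ 1) grade improvement on the WSRS".

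SAP 2.4.2 makes multiple imputation the primary method for missing WSRS in the FAS. Part (i) uses five imputed datasets and a fixed seed. On the model it says: "Linear regression will be employed to model the missing WSRS score, with the following covariates included in the imputation model: treatment and non-missing data", the latter taken before Month 6. Departures from a monotone pattern are handled "with slight deviations being corrected by the Markov Chain Monte Carlo (MCMC) method of the MI procedure". The only link from imputation to analysis is this: "The imputed datasets will be analyzed using the methodology described for the primary analysis of response rates at Month 6".

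SAP 2.4.3 declares non-inferiority when "the upper bound of the interval is less than 15% in both the FAS and PP populations". The PP analysis uses observed cases. LOCF and observed-case rows stand beside the MI row in Table 8-1 as sensitivity analyses.

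The paragraph on MI is not blacked out. Neither it, Protocol 10.6, SAP 2.4.3, SAP 2.8 nor the table shells mention rounding, range limits, cut-points or a categorical model.

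**The concern.** On a whole-grade scale, a one-grade improvement sits exactly on the responder cut. An observed fold in that category is a responder. A continuous draw centred near one grade of improvement falls below the cut about half the time and is then a non-responder. The imputed folds are therefore judged by a stricter rule than the observed ones. The MCMC step does not help, because it also draws from a normal model.

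The MI row is labelled primary, and Tables 8-1 and 8-3 report each product's response rate from it. Two programmers using the same seed could report different primary rates, depending on whether they round. That choice should be fixed before the data are seen.

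**Working it through.** The plan gives no figure to reproduce, and its sample-size text is blacked out. The check asks how often an imputed fold counts as a responder under each reading.

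**Inputs from the documents.** About 175 subjects (Protocol 4.2). Baseline grade 3 on both sides or 4 on both sides (Protocol 5.2). Mean WSRS change -1.1 at Week 24 in the earlier US split-face study (Protocol 2.4.2). In the Restylane Defyne instructions for use, 69.8% with clinically significant improvement at 48 weeks (Protocol Appendix 2, IX), a term that Protocol 7.2 defines as at least one grade.

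**Assumptions.** The grade distribution, the share *m* of folds missing at Month 6, and random missingness unless stated.

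**Closed form.** Let improvement be 0, 1 or 2 grades, with mean μ, SD σ and true response rate p. For a normal draw with the same mean and SD:

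- unrounded response = Φ((μ - 1)/σ)
- response after rounding to the nearest grade = Φ((μ - 0.5)/σ)
- error in the FAS rate ≈ m × (imputed response - p)

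| P(0/1/2 grades) | μ | σ | True | Unrounded | Rounded |
|---|---|---|---|---|---|
| 0.3/0.3/0.4 | 1.10 | 0.83 | 70% | 54.8% | 76.5% |
| 0.22/0.55/0.23 | 1.01 | 0.67 | 78% | 50.6% | 77.6% |
| 0.3/0.6/0.1 | 0.80 | 0.60 | 70% | 36.9% | 69.1% |

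The FAS error in points at 5/10/15% missing is then:

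| P(0/1/2 grades) | Unrounded | Rounded |
|---|---|---|
| 0.3/0.3/0.4 | -0.8 / -1.5 / -2.3 | +0.3 / +0.65 / +1.0 |
| 0.22/0.55/0.23 | -1.4 / -2.7 / -4.1 | 0.0 / 0.0 / -0.1 |
| 0.3/0.6/0.1 | -1.7 / -3.3 / -5.0 | 0.0 / -0.1 / -0.1 |

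For example, 0.10 × (54.8 - 70) = -1.5.

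**Simulation of the actual procedure** (five imputations, regression on treatment, baseline and two earlier visits, both folds missing together):

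- Grades 0.3/0.3/0.4: -0.8/-1.5/-2.3 unrounded and +0.3/+0.65/+0.8 rounded. Grades 0.3/0.6/0.1: -1.7/-3.4/-4.9 unrounded. These agree with the formula.
- True rate 70%, a quarter of responders improving two grades, 10% missing: imputed folds respond in 43% unrounded and 71% rounded. The FAS rate is 67.3% unrounded and 70.1% rounded. Stronger or weaker correlation between visits (0.40 to 0.95) leaves the 43% unchanged.
- A normal latent improvement rounded to grades, true rates 65-85%: -1.3 to -1.5, -2.6 to -3.0 and -3.7 to -4.3 points at 5/10/15% missing.
- A non-monotone pattern (true 78%, 10% missing Month 6, a further 5% missing Month 3 only, chained normal regressions standing in for MCMC): FAS rates of 75.0-75.2% unrounded, against 78.0-78.1% with predictive mean matching.

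**Direction.** A reversal is possible only with almost no one-grade improvers. With 80% at 0 and 20% at 2 grades, truth is 20% and unrounded draws give 22.7%, but the mean improvement there is only 0.4. At mean 1.1 with no one-grade improvers at all (0.45/0/0.55), unrounded draws give Φ(0.1/0.995) = 54.0% against 55%, still slightly low.

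**Effect on the difference.** The shift is m times the gap between the two products' errors, which is zero when they have the same distribution. In simulation with a true difference of 15 points (80% against 65%), the mean estimate moved by 0.3 points or less. False success was 1.2-2.4% in the FAS and 1.2-2.2% in FAS and PP jointly, against a nominal 2.5%. With 65% against 75% and 20% missing, the difference was 9.2 points unrounded, 9.3 rounded and 9.9 with full data.

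**The case against.** The best defence is that nothing decisive depends on this. The declared test is the upper limit of the difference, both rates fall together, and success also needs PP, which involves no imputation. That stands.

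A second defence is that 2.3 is not a grade, so a sensible programmer would round. Perhaps so, but the text sends the imputed datasets directly to the response-rate analysis. If rounding is intended, one sentence settles it.

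A third is that the size rests on quantities the visible documents do not give. This is also right: at a true rate of 70%, the error more than doubles between the distributions 0.3/0.3/0.4 and 0.3/0.6/0.1. A wide range is therefore quoted. Rounding is not exact either, and overshoots where few folds improve by just one grade.

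The sensitivity rows help only partly. Observed cases are a full check only if data are missing completely at random, and the SAP is unclear on that: "The imputation using MI will assume a Missing Completely at Random (MAR) mechanism". When subjects with a non-responding fold at Month 3 were made four times as likely to miss Month 6, the observed-case rates were 0.6 to 2.8 points too high while the unrounded MI rates were too low. LOCF carries whole grades forward, but its accuracy was not examined here.

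A reader might infer two stronger points. One is that the non-inferiority conclusion or its type I error is at risk; the calculations show neither. The other concerns pairing. The covariate list does not name the opposite fold, and the SAP says "it is expected that when a data is missing, it will be missing for both NLFs in most of the cases", so a reader might conclude that pairing is lost in imputed subjects. The SAP does not state the data layout, so the text does not establish this. The grade problem does not depend on it: using both folds as predictors without rounding changed the error by no more than 0.1 point.

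**Conclusion.** The concern holds for the reported response rates and should be fixed. As written, SAP 2.4.2(i) classifies fractional draws against a whole-grade cut and understates both primary FAS rates for any plausible grade distribution. With assumed true rates of 70-78%, the understatement is about 0.8 to 1.7 points at 5% missing, 1.5 to 3.4 at 10% and 2.2 to 5.0 at 15%. It scales with the missing share. The missing share and the grade distribution are assumptions; the mean change of -1.1 only anchors what is plausible. The defect lies in the two rates in the primary table, not in the non-inferiority decision.

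**What to change.** Before database lock, amend SAP 2.4.2(i) so that imputation returns valid grades or response status. Predictive mean matching, ordinal logistic imputation or direct imputation of Month 6 response would each do this. Predictive mean matching was simulated with one record per subject and both folds as predictors; FAS rates were within about 0.15 points of the truth. The other two were not simulated. Use the same kind of method for non-monotone gaps in place of the MCMC step.

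At minimum, add one sentence: each imputed score is rounded to the nearest whole grade and limited to 1-5 before response is derived. In simulation at true rates of 65-85% this left a residual of roughly -0.3 to +0.9 points, depending on the grade distribution.

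Naming the data layout and saying whether the opposite fold is a predictor would be a useful optional clarification. The cost is SAP wording and minor programming; no new data or visits are needed.
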